### **4.2. Data Listing to be Generated**

Listing 1	Ex Vivo Fluorospot
Listing 2	In Vitro stimulated Fluorospot
Listing 3	Ex Vivo Intracellular Cytokine Staining
Listing 4	In Vitro stimulated Intracellular Cytokine Staining
Listing 5	Ex Vivo Dextramer
Listing 6	In Vitro stimulated Dextramer
Listing 7	ctDNA – Signatera Assay
Listing 8	ctDNA – Sysmex Assay

*Elicio Therapeutics, Inc.*  
*Addendum: Immunogenicity and ctDNA Analysis Plan, Protocol ELI-002-001*  
*February 6, 2023, Version 1.0*

---

Table 1  
 Summary and Change from Baseline for ex Vivo Fluorospot  
 (Immunogenicity Population)

Analyte	Antigen	Visit	Value	Statistic	(N=xx)	(N=xx)	(N=xx)	Cohort 1	Cohort x	Cohort x																															
IFNg	[see programming note]		Baseline (1)	Actual	N [2]	Mean (SD)	Median	Min,Max	xx.x	--																															
											N Undetectable [3]	xx.x, xx.x x																													
													Visit x	Actual	N	Mean (SD)	Median	Min,Max	xx xx.x	(xx.xx)	xx.xx																				
																						N Undetectable [3]	xx.x, xx.x x																		
																								Fold Change from Baseline	N	Mean (SD)	Median	Min,Max													
																													Response 1 [4,5] Response	N(%)											
																															2 [4,6]	N(%)									
																																	Repeat for GrB IFNg+/GRB+								
																																	Total [7]								

Results are summarized using the mean of normalized, background subtracted replicates

[1] Baseline is based on Visit 2 result

[2] N reflects the number of patients with detectable result.

[3] Number of subjects with results below the limit of detection. [4] Denominator is number of subjects with results at visit

[5] Response is defined as having a two-fold increase from baseline.

[6] Response is based on bootstrap method described by Moodie [2010] testing for 2-fold difference from the control wells

[7] Total Analyte is the sum of IFN, GrB, and IFN/GrB results for each analyte.

Programming note: For each analyte, antigens will include G12R, G12D, G12V, G12C, G12A, G12S, G13D, total mKRAS (sum of G12R, G12D, G12V, G12C, G12A, G12S and G13D antigens), Master mix NS will not be included in table but will be in the listing.

PROGRAM NAME: XXX

DATE: HH:MM/DDMMYY

Elicio Therapeutics, Inc.  
Protocol ELI-002-001

Confidential

Page 1 of x

Table 2

Summary and Change from Baseline for In vitro stimulated (IVS) Fluorospot  
(Immunogenicity Population)

Repeat layout for table 1.

---

Footnote: Results are summarized using the mean of background subtracted replicates

Programming note : Antigens will include G12R, G12D, G12V, G12C, G12A ,G12S, G13D , WT , master mix, and total mKRAS (sum of G12R, G12D, G12V, G12C, G12A, G12S and G13D antigens). Analytes will include IFNg, TNFa,IFNg+TNFa , and the sum of IFNg TNFa, and IFNg+TNFa NS and CD3 will not be included in Table but should be in Listing.

Protocol ELI-002-001                      Elicio Therapeutics, Inc.                      Confidential                      Page 1 of x

Table 3  
 Summary and Change from Baseline for Ex Vivo Intracellular cytokine staining  
 (Immunogenicity Population)

Antigen	Cytokine	Visit	Value	Statistic	(N=xx)	(N=xx)	(N=xx)	N [2]	Cohort 1	Cohort x	Cohort x	
[see programming note]		Baseline (1)	Actual	Mean (SD)					x			
				Median					xx.x (xx.xx)			
				Min,Max					xx.xx xx.x,			
				N Undetectable					xx.x			
				[3,4]					x	--		
				N								
		Visit x	Actual	Mean (SD)						xx		
				Median					xx.x (xx.xx)			
				Min,Max					xx.xx xx.x,			
				N Undetectable					xx.x x			
				(3)								
				N								
			Fold Change from Baseline									
				Mean (SD)								
				Median								
				Min,Max								

[1] Baseline is based on Visit 2 result

[2] N reflects the number of patients with detectable result.

[3] Number of subjects with results below the limit of detection.

[4] Denominator is number of subjects with results at visit

[5] Total CD4 Response is the sum of CD4: IFNg+ IL2+ TNFa+, IFNg+ IL2- TNFa-, IFNg+ IL2- TNFa+, IFNg+ IL2- TNFa-, IFNg- IL2+ TNFa+, IFNg- IL2+ TNFa-, IFNg- IL2- TNFa+.

Total CD8 Response is the sum of CD8: IFNg+ IL2+ TNFa+, IFNg+ IL2+ TNFa-, IFNg+ IL2- TNFa+, IFNg+ IL2- TNFa-, IFNg- IL2+ TNFa+, IFNg- IL2+ TNFa-, IFNg- IL2- TNFa+.

Programming note: For each analyte, antigens will include, total mKRAS (sum of G12R, G12D, G12V, G12C, G12A, G12S and G13D antigens), G12R, G12D, G12V, G12C, G12A

G12S, G13D, WT,, Master Mix . Each antigen will have the following cytokines : CD4 IFNg, CD4 IL2, CD4 TNFa, CD4 IFNg+ IL2+ TNFa+, CD4 IFNg+ IL2+ TNFa-, CD4 IFNg+ IL2- TNFa+, CD4 IFNg+ IL2- TNFa-, CD4 IFNg- IL2+ TNFa+, CD4 IFNg- IL2+ TNFa-, CD4 IFNg- IL2- TNFa+, Total CD4 cytokine response [5], CD8 IFNg, CD8 IL2, CD8 TNFa, CD8 IFNg+ IL2+ TNFa+, CD8 IFNg+ IL2+ TNFa-, CD8 IFNg+ IL2- TNFa+, CD8 IFNg+ IL2- TNFa-, CD8 IFNg- IL2+ TNFa+, CD8 IFNg- IL2+ TNFa-, Total CD8 cytokine response [5]

Repeat layout by Analyte, Cytokine, and Visit.

Protocol ELI-002-001 Elicio Therapeutics, Inc. Confidential Page 1 of x

Table 4  
 Summary and Change from Baseline In Vitro Intracellular cytokine staining  
 (Immunogenicity Population)

IVS Antigen	Antigen	Cytokine	Visit	Value	Statistic	(N=xx)	(N=xx)	(N=xx)	Cohort 1	Cohort x	Cohort x
		[See programmin g note]	(See Programmin g Note_		Baseline (1)		Actual	N [2] Mean (SD) Median Min,Max N Undetectable	x xx.x (xx.xx) xx.xx xx.x, xx.x x	--	
					Visit x		Actual	[3,4] N Mean (SD) Median Min,Max N Undetectable	xx xx.x (xx.xx) xx.xx xx.x, xx.x x		
							Fold Change from Baseline	(3) N Mean (SD) Median Min,Max			

[1] Baseline is based on Visit 2 result  
 [2] N reflects the number of patients with detectable result.  
 [3] Number of subjects with results below the limit of detection.  
 [4] Denominator is number of subjects with results at visit  
 [5] Total CD4 Response is the sum of CD4: IFNg+ IL2+ TNFa+, IFNg+ IL2+ TNFa-, IFNg+ IL2- TNFa+, IFNg+ IL2- TNFa-,IFNg- IL2+ TNFa+,IFNg- IL2+ TNFa-,IFNg- IL2- TNFa+. Total CD8 Response is the sum of CD8: IFNg+ IL2+ TNFa+, IFNg+ IL2+ TNFa-, IFNg+ IL2- TNFa+, IFNg+ IL2- TNFa-,IFNg- IL2+ TNFa+,IFNg- IL2+ TNFa-,IFNg- IL2- TNFa+.

Programming note: For each analyte, antigens will include G12R, G12D, G12V, G12C, G12A, G12S, G13D, Master Mix, and total mKRAS (sum of G12R, G12D, G12V, G12C, G12A, G12S and G13D antigens). Each antigen will have the following cytokines:  
 CD4 IFNg,CD4 IL2,CD4 TNFa,CD4 IFNg+ IL2+ TNFa+,CD4 IFNg+ IL2- TNFa+,CD4 IFNg+ IL2- TNFa-,CD4 IFNg- IL2+ TNFa+,CD4 IFNg- IL2+ TNFa-,CD4 IFNg- IL2- TNFa+,Total CD4 cytokine response [\*],CD8 IFNg,CD8 IL2,CD8 TNFa,CD8 IFNg+ IL2+ TNFa+,CD8 IFNg+ IL2+ TNFa-,CD8 IFNg+ IL2- TNFa+,CD8 IFNg+ IL2- TNFa-,CD8 IFNg- IL2+ TNFa+,CD8 IFNg- IL2+ TNFa-,Total CD8 cytokine response [\*] Repeat layout by Analyte, Cytokine, and Visit

Table 5

Summary and Change from Baseline for Ex Vivo Dextramer (Immunogenicity Population)

Programming Note: repeat layout for table 3. Replace Antigen column with “Dextramer” and remove IVS antigen and cytokine columns. Only CD8+ dextramer + column from source data will be included.

Table 6

Summary and Change from Baseline for In Vitro Dextramer (Immunogenicity Population)

Programming Note: repeat layout for table 3. Replace Antigen column with “Dextramer” remove IVS antigen and cytokine columns. Only CD8+ dextramer + column from source data will be included.

PROGRAM NAME: XXX

DATE: HH:MM/DDMMYY

Protocol ELI-002-001                      Elicio Therapeutics, Inc.                      Confidential                      Page 1 of x

Table 7  
 Summary and Change from Baseline for ctDNA (ctDNA  
 Population)

Baseline	Baseline (1)	Cohort 1 (N=xx)	Cohort 1 (N=xx)	Cohort 1 (N=xx)
		N (2)	xx	--
		Mean (SD)	xx.x (xx.xx)	
		Median Min,	xx.xx xx.x	
		Max	xx.x	
		N Undetectable (3)	xx.x, xx.x xx	
		<repeat for remaining visits with at least 3 subjects		
Visit 6		N (2)	xx	xx
		Mean (SD)	xx.x (xx.xx)	xx.x (xx.xx)
		Fold Change Mean	xx.xx	xx.xx
		Fold Shange SD- SD	xx.x	xx.x
		Median	xx.x	xx.x
		Min, Max	xx.x, xx.x	xx.x, xx.x
		N Undetectable (3)	xx	xx
Doubling Time	N(4)	Mean (SD)		
		Median		
		Min, Max		
Clearance Duration (weeks)	N(5)	Mean (SD)		
		Median		
		Min, Max		
Response Rate	n%			

[1] Baseline is based on Visit 3 result or Visit 2 if Visit 3 is missing  
 [2] N reflects the number of patients with detectable concentrations of ctDNA .

[3] Number of subjects with results below the limit of detection. [4] N reflects the subjects whose ctDNA doubled.

[5] N reflects subjects whose ctDNA was undetectable or decreased post-baseline.

[REPEAT univariate statistics For VAF + MTM/ML by Assay]

Notes for programming: Timepoints –

- Visits 2, 3 (pre-vaccination)
- Visits 6, 11, 12, 16, 17, 18, 19, 20, 21, 22, 23, 24 (post-vaccination)

Elicio Therapeutics, Inc.  
Protocol ELI-002-001

Confidential

[figure not shown]
Page 1 of x

Figure 1

Ex vivo Fluorospot

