**Table 8: Derived variables**

Variables	Formula
Demographic and Baseline characteristics	
Body mass index (BMI) (kg/m  )	weight (kg)/[height (m)] 
Derivation of Duration	
Study day at any visit	Date of interest – date of first dose of study treatment. One day is added if this difference is ≥ 0
Duration of study (Days)	(Date of study completion/discontinuation (for discontinued subjects) – date of first dose) + 1
Duration of Exposure to the study treatment ( weeks )	Is [last date of booster dose – first date of immunization dose] + 1] / 7. IF treatment discontinuation, then last date of booster dose = last dose date prior to or at the date of treatment discontinuation.
Treatment Exposure and Compliance	
Cumulative Planned volume (mL)	Total planned volume for each dose* Planned number of doses for the duration of exposure
Cumulative actual volume administered (mL)	Total actual volume administered from exposure CRF page (Cumulative value of 'Actual volume administered' from Study Drug Administration)
Expected Dose	Calculated as the expected number of vaccinations multiplied by assigned dose in mg
Compliance (%)	(Cumulative actual volume administered /Cumulative planned volume)*100
Dose intensity (DI) for ELI-002 Amph-Peptides 2P	Amount of actual cumulative dose of ELI-002 Amph-Peptides 2P (mg) divided by expected dose given for a full 10 course of vaccinations.
Dose intensity (DI) for ELI-002 Amph-CpG-7909	Amount of actual cumulative dose of ELI-002 Amph-CpG-7909 (mg) divided by expected dose given for a full 10 course of vaccinations.
Relative dose intensity	Cumulative dose received divided by expected dose and multiplied by 100
Baseline Derivations	
Baseline value	Unless otherwise specified, the baseline value is defined as the last non-missing observation prior to administration of the first dose of study treatment. For most assessments, this would be the Visit 3 value. If Visit 3 is missing, the Visit 2 value will be used.
Change from baseline	Post baseline value – Baseline value
Fold change from baseline	(Post baseline value – Baseline value)/Baseline value
Biomarker Reduction/Clearance	
Note: All reporting will select the biomarker (ctDNA, CEA, or CA-19) which contains the best (i.e., largest decrease post-baseline) result per subject. If there is no decrease for a given subject, then “best” is the smallest increase.	

**Final Analysis  
Statistical Analysis Plan (SAP)**

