**1.9. Missing, Unused, and Spurious Data**

In general, there will be no substitutions made to accommodate missing data points.

For all assays, the limit of quantification (LOQ) will be used if available.

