## **2. STUDY ANALYSES**

### **2.1. Immunogenicity Analysis**

Cellular responses will be characterized by:

- Ex vivo Intracellular cytokine staining
- In Vitro stimulated Intracellular cytokine staining
- Ex vivo Fluorospot
- In vitro stimulated Fluorospot
- Ex vivo Dextramer
- In vitro stimulated Dextramer

Response will be determined in two ways

- Method 1 – For subjects who are negative (below the limit of quantification) at baseline and have a detectable post baseline value (above the limit of quantification) will be considered a responder. For subjects who have detectable baseline values, a two-fold increase from baseline will be considered a responder.
- Method 2 (Fluorospot only)– distribution free resampling (DFR) will be applied using the methods described by Moodie et al 2010. A minimum threshold value of 2-fold difference between control and experimental wells will be assessed.

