#### **2.1.2. Fluorospot**

Actual and increase from baseline values for ex Vivo and in vitro stimulated (IVS) Fluorospot (FS) results will be presented at each timepoint by dose level, assay, and antigen. In addition, the sum of results (IFN $\gamma$ , Granzyme B, and IFN $\gamma$ +Granzyme B for Ex vivo FS and IFN $\gamma$ , TNF $\alpha$ , IFN $\gamma$ +TNF $\alpha$  for IVS) will be calculated for each antigen. Non-stimulated (NS) results will be included in data listings but not tabulated.

Ex vivo (normalized to  $1 \times 10^6$ ) and IVS FS data (non-normalized) will use the background subtracted values for analysis.

Listings will include actual value and absolute and fold-change from baseline and response status according to Method 1 (Section 2.1).

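### Footnote 5 of the addendum's Table 1 shell omits half of the Method 1 response rule, leaving open how subjects undetectable at baseline are scored while they stay in the denominator

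*SAP*

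**What the plan says.** Section 2.1 of the addendum (Immunogenicity Analysis) defines Method 1 in two arms. The first concerns subjects who are below the LOQ "at baseline and have a detectable post baseline value (above the limit of quantification) will be considered a responder". The second reads: "For subjects who have detectable baseline values, a two-fold increase from baseline will be considered a responder". Method 2, distribution-free resampling (DFR), compares experimental wells with control wells and is used for Fluorospot only.

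The Table 1 shell (ex vivo Fluorospot) has a Response 1 row and a Response 2 row. Footnote 5 defines Response 1: "Response is defined as having a two-fold increase from baseline". Footnote 4 sets the base for both rows: "Denominator is number of subjects with results at visit". The Table 2 shell (in vitro stimulated Fluorospot) reuses the Table 1 layout. The shells for Tables 3 to 6 have no response row.

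Three other places bear on the point:

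- Addendum Section 1.9: "For all assays, the limit of quantification (LOQ) will be used if available". It does not say what the LOQ is used for.
- Addendum Section 2.1.2: the Fluorospot listings are to carry "response status according to Method 1 (Section 2.1"). The Listing 1 shell has one response column, based on DFR, and Listing 2 repeats that layout.
- Main SAP Table 8: fold change from baseline is a relative change, ("Post baseline value – Baseline value)/Baseline value".

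**The concern.** The analysis text and the table shell give different rules for the same row. A subject with an undetectable baseline who becomes detectable is plainly a responder under Section 2.1. Under footnote 5 the answer depends on what baseline value enters the fold calculation, which the addendum does not settle. The subject counts in the denominator either way.

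These are the de novo responses, which a vaccine trial most wants to count. The main SAP (Section 13.8.2) assesses pharmacodynamic response through immunogenic response, and pharmacodynamic data are one input to the recommended Phase 2 dose (SAP Section 8.1; Protocol Section 6.1.1). The addendum analyses are run after each cohort (Section 1.8). With 3 to 6 subjects per cohort, the classification of one subject is visible in the reported rate.

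**Working it through.** The plan states no figure to reproduce, so the check compares the two rules case by case.

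**Inputs.** Method 1 is from addendum Section 2.1; the Response 1 definition and denominator are from Table 1 footnotes 5 and 4; the fold-change formula is from main SAP Table 8; the cohort size of 3 to 6 is from SAP Section 8.1. The documents give no LOQ. I set LOQ = 1, so values below are multiples of it.

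**Rules.** Let b be baseline and p the post-baseline value.

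- Method 1: if b < 1, respond when p > 1; otherwise respond when p/b ≥ 2.
- Footnote 5, reading A: replace b by the LOQ when b < 1; respond when p/b ≥ 2.
- Footnote 5, reading B: use raw b; respond when p/b ≥ 2; undefined at b = 0.
- Footnote 5, reading C: as A, but with the Table 8 formula, (p − b)/b ≥ 2, which is p ≥ 3b.

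| b | p | Method 1 | A | B | C |
|---|---|---|---|---|---|
| 0 | 1.2 | yes | no | undefined | no |
| 0 | 1.9 | yes | no | undefined | no |
| 0 | 2.0 | yes | yes | undefined | no |
| 0 | 2.5 | yes | yes | undefined | no |
| 0 | 3.5 | yes | yes | undefined | yes |
| 0.5 | 1.2 | yes | no | yes | no |
| 2 | 3.9 | no | no | no | no |
| 2 | 4.0 | yes | yes | yes | no |
| 2 | 6.0 | yes | yes | yes | yes |

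**What the table shows.**

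1. Under A, subjects undetectable at baseline are classified differently only when p lies between 1 and 2 times the LOQ.
2. Under B with a zero baseline, the ratio does not exist and the shell does not say how to score the subject. Fluorospot values are background-subtracted, so zero is possible.
3. Under C, the disagreement widens to between 1 and 3 times the LOQ. It also reaches subjects with a detectable baseline: at b = 2 and p = 4.0, p/b = 2 but (4 − 2)/2 = 1. The meaning of two-fold therefore has to be fixed as well as the missing arm.

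**Size per subject.** When all cohort members have a result, one reclassified subject moves the rate by 100/6 = 16.7 points (n=6) or 100/3 = 33.3 points (n=3).

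**Illustration with its range.** Take six subjects: four undetectable at baseline who all become detectable, and two detectable at baseline of whom one doubles. Method 1 gives (4 + 1)/6 = 83.3%. If footnote 5 counts k of the four, it gives (k + 1)/6, from 1/6 = 16.7% (k = 0) to 5/6 = 83.3% (k = 4). The composition is invented; the documents give no baseline detection rate.

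**The case against.** The best defence is that footnote 5 is shorthand. The row label, Response 1, mirrors Method 1; footnote 6 abbreviates Method 2 in the same way; and Section 2.1 holds the operative definition. This has some force, but the footnote is written as a complete rule and no shell supplies the missing arm. Section 2.1.2 sends Method 1 status to the listings, yet the Listing 1 shell shows only the DFR column. The shorthand reading therefore does not remove the conflict.

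A second defence is that Section 1.9 lets the LOQ replace an undetectable baseline, so a fold change can be computed. That is a possible reading, and it shrinks the disagreement as shown. The sentence does not mention imputation, however, and the Table 1 shell counts undetectable results separately from the N of detectable ones, which points the other way.

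A reader might go further and infer that subjects undetectable at baseline are scored as non-responders, so that the table always shows the lower rate. The documents do not support this. No sentence scores them so. Under LOQ substitution, anyone reaching twice the LOQ counts under both rules. With a zero baseline, a test coded as p ≥ 2b would pass any positive value. With raw values below the LOQ, footnote 5 could count a rise that stays below the LOQ, which Method 1 would not. A lower rate is the expected direction, not an established one.

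The remaining defences stand and limit the importance. Response 2 does not depend on baseline. The undetectable counts by visit keep a cohort-level shift visible. The endpoint is exploratory (SAP Section 9.1.3), the addendum is mainly descriptive (Section 1.4.1), and no dose rule uses a response-rate threshold.

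**Conclusion.** The inconsistency is real and should be corrected, though it affects one exploratory row in two tables. Footnote 5 leaves out the newly detectable arm of Method 1, so a subject below the LOQ at baseline may be scored as a non-responder or have no defined status.

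The effect ranges from no newly detectable subject to all of them. It is confined to post-baseline values between 1 and 2 times the LOQ if the LOQ is substituted and two-fold means a ratio of at least 2. Without substitution, all newly detectable subjects may be affected. How many subjects that means cannot be derived from the documents, since neither the LOQ nor the baseline detection rate is given. The 83.3% against 16.7% contrast is one end of a range and should not be quoted as the expected effect.

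**What to change.** Replace footnote 5 with the full rule and carry it to Table 2. For example: a responder is a subject below the LOQ at baseline with a post-baseline value above the LOQ, or a subject with a detectable baseline and a post-baseline to baseline ratio of at least 2.

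State in Section 2.1 that the ratio applies only to detectable baselines and is not the Table 8 fold-change formula. Response status then no longer depends on how Section 1.9 is read.

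Add a Method 1 response column to the Listing 1 and Listing 2 shells, as Section 2.1.2 requires, beside the DFR column. Reporting the two arms separately is optional.

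The cost is a reworded footnote, a short clarification, one line of derivation code and one column in two listing shells. No new data are needed.

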### **1.5. Population Definitions**

The following patient populations will be evaluated and used for presentation and analysis of the immunogenicity or ctDNA biomarker data:

- Immunogenicity Population: All patients who receive any amount of study treatment and contribute any immunogenicity data.
- ctDNA Population: All patients who receive any amount of study treatment and contribute any ctDNA data.

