## 2.2. ctDNA

ctDNA response is defined as the absence or reduction of circulating tumor DNA post-baseline. Analysis of ctDNA will be based on results from two laboratories and will be performed separately.

Duration of response is defined as the time in weeks from reduction until the date of increase or presence of ctDNA.

Any patient with detectable ctDNA at baseline whose post-baseline result is less than the baseline value or undetectable will be considered a responder. The number and percentage of responders will be reported.

Doubling will be calculated as the number of weeks between visits where ctDNA first doubles.

Doubling time and response will be based on the tumor molecules per mL (MTM/mL) and Variant Allele Frequency (VAF).

ctDNA levels over time will be summarized using descriptive statistics.

Data listings will present ctDNA values (VAF and MTM/mL) over time, ctDNA response, and duration of response, and time until doubling of ctDNA.

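### Read as written, addendum Table 7 leaves subjects who clear ctDNA out of the visit means and fold changes, and no clear rule for below-limit results overrides it

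*SAP*

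**What the plan says.** In the Table 7 shell of the addendum, the Baseline block and the Visit 6 block each open with an N carrying footnote 2. Mean, SD, median and range follow, and at Visit 6 the fold-change mean and SD as well. The layout is repeated for the remaining visits that have at least three subjects. The footnote says "N reflects the number of patients with detectable concentrations of ctDNA". A separate row gives the undetectable results, with the footnote "Number of subjects with results below the limit of detection".

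The immunogenicity shells (Tables 1, 3 and 4) carry a similar footnote, "N reflects the number of patients with detectable result". There the marker is attached to the Baseline N only; the N for later visits and the N for fold change are unmarked.

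Other parts of the plan bear on the same results:

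- Addendum 1.5 defines the ctDNA Population as "All patients who receive any amount of study treatment and contribute any ctDNA data".
- Addendum 1.9 says "In general, there will be no substitutions made to accommodate missing data points" and then "For all assays, the limit of quantification (LOQ) will be used if available".
- Addendum 2.2 says "Any patient with detectable ctDNA at baseline whose post-baseline result is less than the baseline value or undetectable will be considered a responder".
- Main SAP Table 8 defines clearance as a change of −100% from baseline, and fold change as the post-baseline value minus baseline, divided by baseline.
- Protocol section 11.4 plans a ctDNA fold change at every timepoint, with no condition on detectability.

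**The concern.** Whether ctDNA is detectable after baseline is itself the outcome of interest. If the mean, median and fold change are taken over detectable results only, the subjects with the best result leave the summary at the moment they reach it.

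The set can also shift the other way. Protocol section 7.1, criterion 4, admits subjects on a serum marker alone. A subject with undetectable ctDNA at baseline is then outside the baseline mean but joins a later one if ctDNA turns positive. Each visit therefore averages a different set, and no visit is directly comparable with baseline.

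If the three-subject display rule also uses the detectable N, a visit at which most of a cohort has cleared might not be shown at all.

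Change in biomarker level is a listed exploratory endpoint (SAP 9.1.3), the tables are laid out by dose cohort, and cohorts hold 3 to 6 subjects. One or two clearers can move a cohort mean materially.

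**Working it through.** The plan gives no figure to reproduce. The check is an illustration on **assumed data**: six subjects, baseline 1.0 each; k clear, and the rest split evenly between halving (0.5) and doubling (2.0). Fold change is (post − baseline)/baseline, from main SAP Table 8, because the addendum gives no formula.

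**Two of six clear.**

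- Detectable only (n = 4): mean level (0.5 + 0.5 + 2 + 2)/4 = 1.25; mean fold change (1.25 − 1)/1 = +0.25.
- All six, cleared = 0: 5/6 = 0.833; fold change −0.167.
- All six, cleared at an assumed limit of 0.05: 5.1/6 = 0.850; −0.150.
- All six, cleared at an assumed limit of 0.20: 5.4/6 = 0.900; −0.100.

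The median moves as well: 1.25 in the four detectable subjects, 0.5 in all six.

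**Four of six clear.**

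- Detectable only (n = 2): (0.5 + 2)/2 = 1.25; +0.25, the same as before.
- All six, cleared = 0: 2.5/6 = 0.417; −0.583.
- All six, cleared at 0.20: 3.3/6 = 0.550; −0.450.

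In this example the detectable-only figure does not respond to clearance at all.

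**General form**, with everyone detectable at baseline and cleared = 0: fold change over all = (n_det/n) × F_det − n_cleared/n, where F_det is the detectable-only mean. Check: (4/6) × 0.25 − 2/6 = −0.167. The sign reverses when n_cleared > n_det × F_det. With F_det = 0.25 in six subjects, one clearer gives (5/6) × 0.25 − 1/6 = +0.042 and two give −0.167.

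In a larger group the reversal is less certain. With 2 of 18 clearing, the all-subject result is +0.111 (cleared = 0). With 4 of 18, it runs from −0.028 (cleared = 0) to +0.017 (cleared at 0.20).

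**The passages side by side.** For a subject who clears, addendum 2.2 records a response, main SAP Table 8 records −100%, and Table 7, taken literally, records no level and no fold change. Section 1.9 does not settle this. An undetectable result is not a missing one, and the sentence on the LOQ does not say whether the LOQ is a value to substitute or a threshold. Section 2.1 uses it as a threshold for calling a subject negative. The shells also refer to detection where 1.9 and 2.1 refer to quantification, so a result between the two limits has no clear place.

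**The case against.** The best answer is that footnote 2 only defines a count. No sentence restricts the means to detectable results, the ctDNA Population is wider, and section 1.9 can be read as substituting the LOQ, which would keep clearers in. That reading is possible. But the footnoted N is printed directly above the statistics and the undetectable results have their own row, so the literal reading of Table 7 excludes them. If 1.9 does mean substitution, it and the shell give different results and must be reconciled.

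It is also fair that clearers stay visible: in the undetectable count, the response rate and the clearance-duration N of the same table, in the main SAP's percent change and waterfall plot, and in the listings. The addendum calls its analysis primarily descriptive, and no decision rule uses these means. That limits the consequence; it does not make the summary right.

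Two objections to an obvious remedy also stand. Entering every undetectable ctDNA value as zero leaves fold change undefined for subjects undetectable at baseline. It also breaks the geometric mean required by addendum 1.4.1.

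**Conclusion.** The point holds for Table 7. As written, the ctDNA level at each visit is biased upward, and clearance drops out of the fold change. The size depends on how many subjects clear. The sign reversal rests on assumed values and shows what can happen in a cohort of 3 to 6, not what is likely.

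Three stronger readings are tempting, and the documents do not support them.

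- **That the T-cell means are inflated in the product's favour.** In Tables 1, 3 and 4 the marker sits on the Baseline N only, so post-baseline handling is not stated. If only baseline is restricted, the baseline mean rises and apparent change shrinks. Subjects below the LOQ at baseline who become detectable are responders under Method 1 of addendum 2.1, yet have no usable fold change without a substituted value. The net direction is not established.
- **That the ctDNA tables flatter the product.** Leaving out clearers makes levels and fold changes look worse.
- **That the secondary endpoint is compromised.** The proportion with reduction or clearance counts clearers and is unaffected.

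**What to change.** In Table 7:

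- Make N all subjects with a ctDNA result at the visit, and keep the undetectable count as a sub-count of it.
- Include undetectable results in the mean, median and range, as 0 for these arithmetic summaries. For the geometric mean use a stated LOQ-based value, with a second value as a sensitivity check.
- Report fold change for subjects with detectable baseline ctDNA, with clearance counted as −1 (−100%), in line with main SAP Table 8.
- Base the three-subject display rule on subjects with a result.

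In section 1.9, state one below-limit rule, say whether the LOQ is substituted or used as a threshold, and apply the rule to baseline, visit and fold-change rows of the immunogenicity shells. Use either detection limit or quantification limit throughout.

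This is a text and programming edit that needs no new data. The small cost is that the geometric means, and any immune summaries that use substitution, will depend on the substituted value; the sensitivity value shows by how much.
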